3. STUDY DESIGN

This study will use a double-blind, placebo-controlled design with all subjects receiving all zolmitriptan and cocaine doses (i.e., zolmitriptan and cocaine dose are within subject factors) in a randomized order.

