4. STUDY POPULATION

Up to 200 individuals will be screened to participate in this study. We intend to admit/enroll 30 (15 male and 15 female) subjects to ensure we have 20 completers (10 male and 10 female) in the study. These individuals must be English-speaking, English-reading subjects 18 – 55 years of age of varying ethnic backgrounds and they will be recruited to participate as inpatients for approximately one month. Enrollment in this study will occur between September 1, 2021, and August 31, 2023. Subjects will be required to provide legal proof of age.

Inclusion Criteria:

1. Able to speak/read English,
2. Not seeking treatment for drug use at the time of the study,
3. Female or male between the ages of 18 and 55 years,
4. Report recent illicit use of cocaine (i.e., within the last week) via the smoked or intravenous route,
5. Recent cocaine use verified by benzoyllecgonine positive urine, as well as fulfillment of DSM-5 diagnostic criteria for cocaine use disorder,
6. Judged to be medically and psychiatrically healthy other than the diagnosis for cocaine use disorder at the time of the interview by study physicians,
7. ECG, read by a cardiologist, within normal limits,
8. Not taking monoamine reuptake inhibitors (including SSRIs), monoamine oxidase inhibitors (other than cocaine), or cimetidine (contraindications to zolmitriptan),
9. No diagnosis of phenylketonuria (contraindication to zolmitriptan),
10. Females using an effective form of birth control and not pregnant or breast feeding. A pregnancy test will be conducted daily during study participation to ensure female subjects do not contain in the study if pregnant. For this protocol, effective birth control is considered to be: abstinence from heterosexual intercourse, hormonal contraceptives (birth control pills, injectable/implant/insertable hormonal birth control products, transdermal patch), intrauterine device (with or without hormones) or double barrier method (e.g., condom and spermicide) during participation and for at least 30 days after the last dose of study medication or surgical sterilization.
11. No other known contraindications or allergies to zolmitriptan.
12. Subjects must have a BMI less than or equal to 30.

Exclusion Criteria:

1. Chemistry values or screening outcomes including outside normal ranges that are deemed by the study physicians to be clinically significant. Lipid levels are included in this protocol as an additional check for cardiovascular health.

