5-7	Experimental Sessions 1-3. Subjects complete 1 sample and 5 choice trials to receive cocaine (0, 10 and 30 mg/70 kg) or money (\$6.00) by responding on the concurrent progressive-ratio schedule. Assessment battery completed following administration of the sampling dose as described below.
8-9	Washout. Placebo administered twice daily (0700 and 1900 hours).
10-15	Zolmitriptan (2.5 mg/day) maintenance. Administered in divided doses (0700 and 1900 hours).
13-15	Experimental Sessions 4-6. Details are the same as for days 5-7.
16-17	Washout. Placebo administered twice daily (0700 and 1900 hours).
18-23	Zolmitriptan (5 mg/day) maintenance. Administered in divided doses (0700 and 1900 hours).
21-23	Experimental Sessions 7-9. Details are the same as for days 5-7.
24-25	Washout. Placebo administered twice daily (0700 and 1900 hours).
26-31	Zolmitriptan (10 mg/day) maintenance. Administered in divided doses (0700 and 1900 hours).
29-31	Experimental Sessions 10-12. Details are the same as for days 5-7.
32	Discharge.
Note	Dosing order is illustrative. All doses will be administered in random order.

This experiment will require each subject to participate for approximately one month. Experimental sessions will be conducted as outlined in Table 1 above. We would like to note four important points relating to the table above: 1) To avoid experimental testing on weekends, subjects may be maintained on zolmitriptan or placebo for longer than outlined above (i.e., maintenance conditions may last for two days longer than in the example above). 2) The order of zolmitriptan maintenance conditions and cocaine experimental sessions will be randomized. 3) All maintenance conditions will be followed by a two-day washout period in which the participant receives a placebo delivered in a double-blinded fashion. 4) If subjects leave the protocol for a reason unrelated to study procedures (e.g., a family emergency or dental problems), they may be re-admitted

with physician approval to complete the remainder of the protocol, picking up in the condition where they left off (i.e., sessions/dose conditions that have already been completed will not be repeated). Thus, they may not complete the protocol over one approximately 33-day admission but can complete the protocol over two admissions totaling approximately 33 days.

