Data Analysis. All data will be analyzed statistically as outlined below using SPSS. Only data from completing subjects will be included in the analyses. Any subjects who do not complete the study will be replaced until we accrue 20 completers. Statistical significance refers to $p \leq 0.05$.

Aim 1: Demonstrate that 5-HT_{1b} activation reduces the reinforcing effects of cocaine. The reinforcing effects of cocaine will be determined by evaluation of break points for cocaine and money from the concurrent progressive-ratio choice task. For cocaine and money break points, each of which have one data point for each dose condition, data will be analyzed using two-factor repeated-measures ANOVA. Cocaine (0, 10, and 30 mg/70 kg) and zolmitriptan (0, 2.5, 5, and 10 mg/day) will be factors for these analyses. A significant augmentation (i.e., leftward shift in the dose-response curve) or attenuation (i.e., rightward shift in the dose-response curve) of the effects of cocaine will be inferred if the main effect of the zolmitriptan or the cocaine-zolmitriptan interaction attains statistical significance in the ANOVA. If the cocaine-zolmitriptan interaction attains statistical significance, the Mean Square Error (MSE) term will be used to conduct Tukey's HSD *post-hoc* test to make appropriate pair-wise comparisons between means.

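### Dose order is random with no stated balancing, replacements have no sequence rule and the ANOVA has no period term; a Williams square together with a period factor is a cheap improvement

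*Combined protocol and SAP*

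**What the plan says.** Section 3 describes a complete within-subject design, "with all subjects receiving all zolmitriptan and cocaine doses". On order, the numbered notes after Table 1 in Section 7 say "The order of zolmitriptan maintenance conditions and cocaine experimental sessions will be randomized", and the note inside the table says "Dosing order is illustrative. All doses will be administered in random order". Section 3 and the Drug Dose and Administration paragraph add only that order is randomised. Nothing in the document mentions blocking, counterbalancing, a Latin or Williams square, or sequence groups.

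Under Data Analysis in Section 7, "Only data from completing subjects will be included in the analyses", and "Any subjects who do not complete the study will be replaced until we accrue 20 completers". No rule says which order a replacement receives. Section 4 plans 30 enrolled "to ensure we have 20 completers (10 male and 10 female) in the study".

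The primary model is a two-factor repeated-measures ANOVA: "Cocaine (0, 10, and 30 mg/70 kg) and zolmitriptan (0, 2.5, 5, and 10 mg/day) will be factors for these analyses". Period, sequence and preceding dose are not in it. On carryover, the plan has two days of placebo after each condition and three days on each new dose before testing.

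**The concern.** Each subject spends about a month as an inpatient and completes twelve sessions of the same tasks. Practice, familiarity with the choice task and the effects of confinement could shift break points and impulsivity scores over the four periods. Note 4 to Table 1 also allows completion over two admissions. If one dose happens to fall late more often than another, part of that shift enters the dose difference. The planned model has nothing to absorb it.

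Balance is available at almost no cost, because 20 completers divide exactly into four sequences of five. At stake is the precision of the zolmitriptan comparisons, and how far a reader can trust that an observed dose difference is not partly a difference in calendar position.

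**Working it through.** **Inputs from the documents.** Four zolmitriptan conditions, hence four periods (Table 1); 20 completers (Section 4 and Data Analysis); f = 0.27, alpha 0.05, power 80% (Power Analysis).

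**Assumptions.** One value per subject per maintenance condition; sphericity; within-subject correlation 0.5; orders that are independent random permutations; linear drift of b residual SD per period, with b from 0 to 1. The documents give neither the correlation nor the drift.

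**1. The plan's own figure.** The noncentrality is λ = f²·N·m/(1−ρ) = 0.27² × 20 × 4/0.5 = 11.664. With df 3 and 57 the power is 79.95%, so the stated 80% reproduces for the zolmitriptan main effect at ρ = 0.5. It is 64.1% at ρ = 0.3 and 96.0% at ρ = 0.7. A one-way layout of 12 cells at ρ = 0 gives 79.7%, so the stated figure does not identify its basis uniquely.

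Under equally spaced dose means with step d, 5d² = 11.664/20 = 0.5832, so d = 0.3415. The 10 mg/day versus placebo difference is then 3d = 1.02 residual SD.

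**2. Imbalance under independent random orders.** There are 4! = 24 orders. Balance would be 20/4 = 5 subjects per dose in each period, and 60 transitions/12 ordered pairs = 5 per pair. In 100,000 simulated schedules of 20 subjects:
- exact period balance never occurred;
- the smallest dose-by-period count averaged 1.9 and the largest 8.6;
- some count was 2 or fewer in 78%;
- counts of which dose preceded which ran on average from 2.0 to 8.4.

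For two doses in one subject, the variance of the difference in period is 2 × (1.25 + 1.25/3) = 3.333. Over 20 subjects the SD of the mean difference is √(3.333/20) = 0.41 periods. The difference exceeds half a period in 20% of schedules.

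**3. Effect on the 10 mg/day versus placebo contrast.** Without a period term, its variance in residual SD units is 2/20 + b² × 3.333/20.

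| Drift b | Random orders: SD | Square: SD |
|---|---|---|
| 0 | √0.1000 = 0.32 | 0.32 |
| 0.25 | √0.1104 = 0.33 | 0.32 |
| 0.5 | √0.1417 = 0.38 | 0.32 |
| 1.0 | √0.2667 = 0.52 | 0.32 |

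Simulation agrees. Random orders with a period term give about 0.33 at every drift.

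**4. Effect on the planned F test.** Simulated power at f = 0.27 and type I error, without a period term (20,000 trials per cell in the middle rows, 3,000 in the outer rows):

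| Drift b | Random: power / type I | Square: power / type I |
|---|---|---|
| 0 | 79% / 5.4% | 79% / 4.2% |
| 0.25 | 75.3% / 4.8% | 75.5% / 3.2% |
| 0.5 | 63% / 4.9% | 61% / 1.2% |
| 1.0 | 38% / 5.5% | 15% / below 0.1% |

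With a period term, power is about 80% for the square at every drift tried, and about 77% to 78% for random orders.

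**5. Why the square alone is conservative.** It takes drift out of the dose means but leaves it in the error. At b = 0.5 the period sum of squares is 20 × 0.5² × 5 = 25. The expected error sum of squares rises from 57 to 82, and the mean square by 82/57 = 1.44, with no matching rise in the numerator.

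**6. Cost of the period term.** It takes three of the 57 error degrees of freedom. With df 3 and 54, power at f = 0.27 is 79.8%, against 79.95%.

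**The case against.** The documents do not say that simple randomisation was chosen. A blocked or Latin-square list held by the Investigational Drug Service would fit the wording, and every imbalance figure above depends on the assumption of independent orders. Random orders are also valid: they give no bias in expectation and hold type I error near 5%. At a drift of 0.25 residual SD per period the contrast SD rises only from 0.32 to 0.33. Washout and run-in already target carryover, with about 1.5 days quoted for steady state against three days allowed, and a practice session precedes any data. The period term does most of the work under either allocation. Ten per sex does not divide by four, and six cocaine orders divide neither 20 nor 80. Four sequences are easier to guess than 24.

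Most of this stands, and it limits the size of the point. It does not remove it. Nothing in the plan secures balance, and nothing in the model absorbs a time trend. Washout and run-in address residual drug, not practice or time in confinement. The sex split is no obstacle: 3, 3, 2, 2 in one sex and 2, 2, 3, 3 in the other gives five per sequence.

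A reader might infer that zolmitriptan dose will be confounded with period, so that the results are biased or the error rate inflated. The documents do not support that. They leave the allocation method open, and even unrestricted random orders produce chance imbalance that adds variance, not bias.

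**Conclusion.** The point holds as a cheap improvement, not as a flaw that threatens validity. The plan randomises order without stating any balancing, has no sequence rule for replacements and omits period from the model. If orders are independent permutations, the loss ranges from none at zero drift to a contrast SD of about 0.52 instead of 0.32 at one residual SD per period. Power under the planned ANOVA falls to 63% at a drift of 0.5. These sizes rest on the assumed linear drift, a correlation of 0.5 and sphericity.

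It would also be wrong to conclude that a balanced square is sufficient on its own, or that imbalance is being accepted with no safeguard at all. The square without a period term yields no more power and an over-conservative test, and the washout and run-in are real protection against carryover.

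**What to change.** State the randomisation method, and make these four changes together:

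1. Allocate zolmitriptan order from a four-sequence Williams square, with five completers per sequence. Each dose then falls in each period five times, and each ordered pair of consecutive doses occurs five times.
2. Give each replacement the sequence of the subject replaced. Without this rule, 30 enrolled with 20 arbitrary completers lose the balance: contrast SD is about 0.33 at drift 0.5 and 0.37 at drift 1.0 without a period term.
3. Balance the six cocaine session orders as nearly as possible. Over 20 × 4 = 80 condition blocks that is 13 or 14 uses of each order.
4. Add period as a factor in the zolmitriptan analyses. Do not adopt the square without it.

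The cost is a new list from the investigational pharmacy and three error degrees of freedom (power 79.95% to 79.8% at f = 0.27). No subjects or visits are added. The downside is fewer possible orders, so the set of sequences should be withheld from staff who see subjects.

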Aim 1: Demonstrate that 5-HT_{1b} activation reduces the reinforcing effects of cocaine. The primary hypotheses, related to our first specific aim, are that: 1) cocaine will function as a reinforcer on the concurrent progressive-ratio choice task that was developed and validated in our laboratory ([name] et al., 2016; 2020) and 2) zolmitriptan will attenuate the reinforcing effects of cocaine, leading to the reallocation of behavior towards the non-drug alternative (i.e., \$6.00) available on the choice task.

Aim 2: Demonstrate that 5-HT_{1b} activation attenuates subjective abuse-related effects of cocaine (e.g., positive subjective effects, craving). The primary hypotheses related to our second specific aim are that: 1) cocaine will produce prototypic effects on subjective outcomes (e.g., increased ratings of drug liking) and 2) zolmitriptan will attenuate these effects (e.g., reduce cocaine related increases on ratings of drug liking).

Aim 3: Demonstrate that 5-HT_{1b} activation attenuates impulsive responding that is a common characteristic of cocaine use disorder and is mediated by the 5-HT system. The primary hypothesis related to our third specific aim is that zolmitriptan will attenuate impulsive responding (e.g., reduce delay discounting of drug and money). This hypothesis is based upon our previous findings and the preclinical outcomes described above.

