2. OBJECTIVES

The primary objective of this study is to demonstrate that 5-HT_{1b} agonism reduces motivation to earn cocaine doses on a progressive-ratio schedule of reinforcer availability (a widely accepted measure of motivation) in

active cocaine users. We will also include a battery of subject-rated, cognitive behavioral and physiological measures to have a fuller profile of 5-HT_{1b} agonism on the effects of cocaine.

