Self-Administration Task. After sampling the intravenous cocaine dose (0, 10, and 30 mg/70 kg), subjects will complete 5 choice trials between that dose and \$6.00, separated by 60 minutes. The money amount was selected based on previous research because it functions as a reinforcer but does not completely suppress drug-taking behavior ([name] et al., 2020). The initial response requirement for either choice (i.e., cocaine or money) will be 400 mouse clicks. Response requirements will increase by 200 responses for previously chosen options. For example, if a subject chooses cocaine at the first opportunity, the next response requirement for cocaine would be 600 responses, but the response requirement for money would remain at 400 responses. If a subject were to choose one option exclusively, the response requirements would be 400, 600, 800, 1000 and 1200 responses. These response requirements were based on our previous human laboratory studies that have tested various ratio parameters to maximize drug-maintained responding while minimizing placebo self-administration ([name] et al., 2016; 2020; Sevak et al., 2010; [name] et al., 2010). Subjects may choose not to complete a ratio for either reinforcer during a choice trial (i.e., an omission), but physiological measures and the assessment battery will still be completed as scheduled and the ratio requirements for each reinforcer will carry forward to the next trial. Break points for cocaine and money will be the primary outcome variables.

Assessment Battery. A battery of subjective and cognitive tasks will also be used to assess drug effects to meet Aims 2 and 3. Standard safety and tolerability measures will also be included.

Subjective Outcomes (Appendix A). Two valid and widely used questionnaires that measure various aspects of mood and drug effects will be included: 1) Drug-Effect Questionnaire ([name] et al., 2003) and 2) Adjective Rating Scale (Oliveto et al., 1992). The Cocaine Craving Questionnaire (Dudish-Poulsen and Hatsukami, 1997) will also be included. These measures will be completed prior to each cocaine sampling dose and at 15-minute intervals after administration of the sampling dose.

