17. DATA AND SAFETY MONITORING

Data Monitoring Plan

Data will be collected using a computerized data collection and management system wherever possible. This system automates the collection of data, which ensures the accuracy and completeness of data collection. The data are stored in a unique file on the hard drive of the computer and are printed after all the tasks are completed. In all instances, the data files do not contain the name of the subject, but instead, a unique four-digit number identifies each subject. A computer file linking the unique number with the subject's name will be kept on a stand-alone, password-protected computer. All data requiring hand entry (e.g., cardiovascular measures) will be double entered by two separate staff members and comparison macros run to ensure accuracy. Data files for experimental tasks and physiological measures from each experimental session will be manipulated and combined into a single electronic spreadsheet for each subject by the PI. Data for all subjects will then be combined into a single electronic spreadsheet and separated by experimental measure for statistical analysis.

The primary outcomes will be the break points for drug and money in the cocaine self-administration task, analyzed as a function of zolmitriptan maintenance conditions. Secondary outcome measures will be abuse-related subjective and cognitive effects of cocaine, analyzed as a function of zolmitriptan maintenance conditions. Tertiary outcome measures will be the physiological and side-effects of cocaine, analyzed as a function of zolmitriptan maintenance conditions. Data will be analyzed using repeated measure ANOVA. The alpha level will be set at 5%.

As noted above, wherever possible, data are collected using an automated computer system, which increases the accuracy and completeness of data collection and ensures the validity and integrity of the data. The initial data manipulation described above will be conducted twice and compared. The quality of manipulated data and data analyses will be monitored by random inspection by the PI and/or Co-Investigators.

Safety Monitoring Plan

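### Aim 1 has two unranked primary outcomes and an either/or test on each, so its false-positive rate is about 10–18% in either direction (about 5–9% for attenuation), not 5%

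*Combined protocol and SAP*

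**What the plan says.** - Section 7, Self-Administration Task: "Break points for cocaine and money will be the primary outcome variables". Section 17, Data Monitoring Plan, repeats this: "The primary outcomes will be the break points for drug and money in the cocaine self-administration task". Neither place ranks the two.
- Section 7, Data Analysis, Aim 1: each break point has its own 3 × 4 repeated-measures ANOVA (three cocaine doses, four zolmitriptan doses). Augmentation or attenuation "will be inferred if the main effect of the zolmitriptan or the cocaine-zolmitriptan interaction attains statistical significance in the ANOVA". Augmentation is defined as a leftward and attenuation as a rightward shift of the dose-response curve. Tukey's HSD compares pairs of means, and only after a significant interaction.
- Significance is p≤0.05 (Section 7, Data Analysis), and Section 17 sets alpha at 5%. The Power Analysis uses 0.05 without naming an outcome or a test.
- Section 2 states the objective in terms of cocaine alone: that 5-HT1b "agonism reduces motivation to earn cocaine doses on a progressive-ratio schedule of reinforcer availability". The Aim 1 hypothesis in Section 1 is that "zolmitriptan will attenuate the reinforcing effects of cocaine, leading to the reallocation of behavior towards the non-drug alternative".
- Section 7 lets a subject complete neither ratio on a trial (an omission). It does not state the break point recorded for an option that is never chosen in a session.

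**The concern.** Two outcomes with two qualifying F tests each give four routes to a positive Aim 1. The documents do not say whether one or both outcomes must succeed, which F test decides, or how the tests are controlled together. Tukey's HSD works inside one ANOVA and does not cover the choice between F tests or between outcomes.

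Two things are at stake. A reader cannot tell in advance what a positive Aim 1 would be: a significant money break point with nothing on cocaine would qualify. And the error rate of the rule as written is higher than the 5% that the plan quotes.

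**Working it through.** **1. The plan's own figure.** The Power Analysis gives f = 0.27 for 80% power with 20 completers at alpha 0.05. For a within-subject factor, the noncentrality is λ = n·m·f²/(1−ρ). With n = 20, m = 4 zolmitriptan levels and ρ = 0.5 (m and ρ are assumptions), λ = 20 × 4 × 0.0729/0.5 = 11.66. On F(3, 57) this gives 79.95% power. Taking m = 12 and ρ = 0 fits almost as well (79.7%). The stated power therefore matches one F test at 0.05.

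**2. Closed-form limits with no zolmitriptan effect.**
- One outcome, either of two independent F tests: 1 − 0.95² = 9.75%.
- Two outcomes that mirror each other exactly: still 9.75%.
- Two independent outcomes: 1 − 0.95⁴ = 18.5%.
- Hypothesised direction only, counting half of each test's 5%: 1 − 0.975² = 4.9% (mirror) to 1 − 0.975⁴ = 9.6% (independent).

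**3. Where the two outcomes lie between these limits.** Take break point as the last completed ratio, 400 + 200(k−1) for an option chosen k times. With no omissions, the two counts sum to 5. If k = 0 is scored 200 (one step below 400), the two break points always sum to 400 + 200 × 5 = 1400 and the correlation is −1. If k = 0 is scored 0, that identity fails and the correlation is −0.95 to −0.97. With 30% omissions it is −0.57 to −0.65.

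**4. Simulation of the choice task.** Inputs from the plan: 20 subjects, 3 × 4 within-subject design, five choices per session, the ratio schedule, and the two F tests at 0.05. Assumptions: three sets of cocaine-choice probabilities across the doses, (0.2, 0.5, 0.7), (0.1, 0.4, 0.8) and (0.3, 0.5, 0.6); subject SD 1.0 on the logit scale; omission rates and k = 0 scores as in the table. There were 20,000 trials per scenario and 24 scenarios. The attenuation columns also require mean cocaine break point at 10 mg/day to be below placebo.

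| Omissions | Any of four tests, k=0 scored 200 | Any of four, scored 0 | Attenuation, scored 200 | Attenuation, scored 0 |
|---|---|---|---|---|
| 0% | 9.6–9.9% | 12.4–13.6% | 4.6–4.8% | 6.2–6.8% |
| 2% | 12.8–13.0% | 13.7–15.2% | 6.2–6.3% | 6.5–7.5% |
| 10% | 15.4–16.6% | 15.9–17.0% | 7.4–7.9% | 7.7–8.4% |
| 30% | 17.7–18.4% | 17.8–18.0% | 8.7–9.1% | 8.6–9.0% |

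Cocaine break point alone under the either/or rule gives 9.3–10.4%.

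A second simulation used a different choice model, with k = 0 scored 0. It defined direction as the mean of the active zolmitriptan doses against placebo, in the hypothesised direction for each outcome. It gave 13–14% with no omissions, 14–15% with about 5% and 18% with 20–40%. Its directional rate was 6.8–9.9%.

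**5. The alternatives under the same null, on cocaine break point only.**
- Main effect alone: 4.6–5.2% in either direction.
- Interaction alone: 4.8–5.6%.
- Holm on both: 4.5–5.3%.
- Either/or rule kept, with the attenuation direction required: 4.5–5.1%.

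**The case against.** The best case for the plan has four parts.

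- **The hypothesis is attenuation.** A false augmentation would not support it, so the directional figure is the relevant one, and with no omissions and k = 0 scored 200 it is 4.6–4.8%. This is fair and is why both figures are given. But the Aim 1 rule also lets augmentation be inferred, so the two-direction rate is what the rule produces. A two-sided 5% test allows about 2.5% in each direction, so 5–9% is not nominal on that basis either.
- **Stricter readings bring the rate down.** If an interaction counts only when a Tukey comparison shows attenuation at an active cocaine dose, and a main effect only when its own outcome moves the right way, the rate is 2.6–5.4%. If both outcomes must be significant in the hypothesised direction, it is 0.5–4.8%. Neither rule is written. The inference is attached to the F test, before Tukey, and reallocation is a hypothesis, not a success criterion.
- **The upper end needs many omissions.** No document supports a particular rate, and the ratios and the money amount were chosen to sustain responding, so omissions may be few. This stands as a limit on the size. At 0–2% omissions the range is 9.6–15.2% in either direction and 4.6–7.5% for attenuation.
- **Naming one test can be expensive, and Section 2 already points to cocaine.** The cost is real and is set out with the fix. Section 2 does favour cocaine, but Sections 7 and 17 expressly make both outcomes primary, and cocaine alone still leaves about 10% in either direction.

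**Conclusion.** The concern holds. As written, Aim 1 does not run at the 5% that the plan states. Its rate is about 10% for cocaine break point alone and up to about 18% once money break point also counts, in either direction. For false support of the hypothesis it is about 5–9%, and it exceeds 5% only if some omissions occur or a never-chosen option is scored 0.

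The lack of a success rule can be read directly from the text. The exact size rests on assumed omission rates, choice probabilities, the k = 0 score and the definition of direction. The simulations add no departure from sphericity beyond what discrete break points produce. The plan states no sphericity correction, and a stronger departure could raise the rates. Nothing in the conduct of the study is affected, but the plan should be changed before the data are analysed.

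**What to change.** **Change to the SAP wording:**
1. Make cocaine break point the single primary outcome, in line with Section 2, and money break point supportive evidence of reallocation.
2. Name either the zolmitriptan main effect or the interaction as the confirmatory test at 0.05. If both patterns must count, use Holm on the two tests (first step 0.025), which holds 5% in either direction.
3. State that a claim of attenuation also requires the effect to be in that direction.
4. State the break point assigned when an option is never chosen.

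If the team wants 5% for a false attenuation claim only, items 1, 3 and 4 with the either/or rule are enough (4.5–5.1%). Holm or a single test is needed only if 5% is meant in either direction.

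**Cost.** A result on money break point alone no longer counts as primary success. The power cost depends on the pattern of the effect. The table assumes Gaussian data and a linear zolmitriptan trend, with effects sized so that the either/or rule on one outcome has about 80% power.

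| Effect present at | Main effect alone | Interaction alone | Holm on both |
|---|---|---|---|
| All cocaine doses equally | 80% | 5% | 72% |
| Both active doses | 72% | 31% | 69% |
| One active dose | 43–44% | 64–65% | 68% |

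At the plan's f = 0.27, testing at 0.025 instead of 0.05 lowers power from about 80% to 71% (m = 4, ρ = 0.5; m = 12, ρ = 0 gives the same).

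Aim 2 names no key measure and applies the same either/or rule to peak effect and AUC. Its results should be labelled secondary and unadjusted for multiplicity, or adjusted.

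### Cocaine and money break points are both primary, each tested at 0.05 with no rule linking them, while the primary objective concerns work for cocaine only

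*Combined protocol and SAP*

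**What the plan says.** Section 7 (Self-Administration Task) states: "Break points for cocaine and money will be the primary outcome variables". Section 17 (Data Monitoring Plan) repeats it: "The primary outcomes will be the break points for drug and money in the cocaine self-administration task".

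The primary objective in section 2 is narrower. It is to show that 5-HT1b agonism "reduces motivation to earn cocaine doses on a progressive-ratio schedule of reinforcer availability". Money does appear in section 1, where the second Aim 1 hypothesis expects zolmitriptan to weaken cocaine reinforcement, "leading to the reallocation of behavior towards the non-drug alternative".

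Section 7 (Data Analysis, Aim 1) analyses each break point in a separate two-factor repeated-measures ANOVA (three cocaine by four zolmitriptan levels). The inference rule covers both outcomes and both directions of shift. A finding "will be inferred if the main effect of the zolmitriptan or the cocaine-zolmitriptan interaction attains statistical significance in the ANOVA". Significance is p ≤ 0.05 in section 7, and section 17 agrees: "The alpha level will be set at 5" per cent. Neither section orders the two outcomes, divides alpha between them, requires both to succeed, or says how the two results together would establish reallocation.

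**The concern.** Two outcomes tested at the full 5% give two routes to a positive primary result, and one of them does not measure the stated primary objective.

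Take a subject with one cocaine choice in a session under both placebo and zolmitriptan, who omits no trial under placebo and two under zolmitriptan. Cocaine break point is 400 both times, while money break point drops from 1000 to 600. Work for cocaine has not changed. If that pattern were common enough to make the money ANOVA significant, the Aim 1 rule would report a changed effect of cocaine. Such a fall in responding is not far-fetched: section 9 lists drowsiness and weakness among the common side effects of zolmitriptan.

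At the other extreme, with few omissions, the two outcomes carry nearly the same information, and a reader of the results could take one finding for two. The plan says what to conclude in neither case.

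**Working it through.** **The plan's own figure.** Section 7 (Power Analysis) gives 80% power at f = 0.27 with 20 completers and alpha 0.05. For the zolmitriptan main effect (four levels, df 3 and 57), λ = f²·n·m/(1 − ρ) = 0.0729 × 20 × 4 / 0.5 = 11.66, which gives power 0.7995. The figure reproduces if ρ = 0.5 and sphericity holds. The documents state neither, so both are assumptions. The calculation covers one outcome at alpha 0.05.

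**How the outcomes are related.** The schedule in section 7 starts at 400 clicks and adds 200 per previous choice of that option, over five trials. The documents do not define break point numerically. I read it as the last completed ratio: 0 for no choices, 200 + 200n for n choices. With no omissions, money choices are 5 minus cocaine choices.

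| Cocaine choices | Cocaine break point | Money break point | Sum |
|---|---|---|---|
| 0 | 0 | 1200 | 1200 |
| 1 | 400 | 1000 | 1400 |
| 2 | 600 | 800 | 1400 |
| 3 | 800 | 600 | 1400 |
| 4 | 1000 | 400 | 1400 |
| 5 | 1200 | 0 | 1200 |

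Over these six pairs, equally weighted, both means are 666.7, the sum of cross-products is -906,667 and each sum of squares is 933,333. So r = -906,667/933,333 = -0.971.

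Section 7 allows omissions. A cocaine break point of 400 then pairs with money break points of 1000, 800, 600, 400 or 0 for zero to four omitted trials.

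**Reference values.** For two independent tests at 0.05, 1 − 0.95² = 0.0975. For four, 1 − 0.95⁴ = 0.185. Whatever the correlation, two tests at 0.05 cannot exceed 0.10.

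**Null simulation.** I simulated 20,000 trials per setting, each with 20 subjects, 12 cells and five choice trials per cell, and no zolmitriptan effect. The assumed log-odds of choosing cocaine were -2.5, -0.7 and 0.5 at the three cocaine doses, with between-subject SD 1.0 and between-session SD 0.5. Omission log-odds varied with the same SDs. The full rule means main effect or interaction.

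| Trials omitted | r | Cocaine main effect | Either main effect | Cocaine, full rule | Either outcome, full rule |
|---|---|---|---|---|---|
| 0% | -0.97 | 0.052 | 0.068 | 0.103 | 0.138 |
| 8% | -0.88 | 0.051 | 0.082 | 0.098 | 0.155 |
| 14% | -0.81 | 0.052 | 0.089 | 0.102 | 0.172 |
| 25% | -0.70 | 0.052 | 0.092 | 0.101 | 0.177 |

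With choices closer to even at every dose and no omissions, the either-main-effect figure falls to about 0.06. The working range is therefore about 6-10%, against 5%.

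**Share due to the second outcome.** On the main effect it adds 0.068 − 0.052 = 1.6 points with no omissions and 0.092 − 0.052 = 4.0 points at 25% omissions. On the full rule it adds 0.138 − 0.103 = 3.5 to 0.177 − 0.101 = 7.6 points. The rest of the full-rule figure, about 10%, is already there with cocaine alone.

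**Cost of the remedies.** With cocaine as sole primary, power stays at 0.80 at f = 0.27. If both outcomes stay primary at 0.025 each, power falls to 0.706, the detectable f rises to 0.296, and 24 completers are needed to regain 80%. At the cited f of 0.54, power stays above 0.999 under either choice.

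**The case against.** Four points count on the other side.

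- **Money belongs to Aim 1.** A reader of section 2 alone might infer that money break point is foreign to the trial. Section 1 makes a shift towards the money alternative part of an Aim 1 primary hypothesis. This stands: money should stay in the plan as a formally tested outcome. It does not justify an unlinked second primary.
- **The outcomes are not strict complements.** A reader might infer from the schedule that money break point only mirrors cocaine break point. Omissions are expressly allowed, and even without them the sums are 1200 or 1400, not constant. This stands.
- **Reallocation does not go untested.** Money has its own ANOVA. Under the last-completed reading, the two break points together give the number of omitted trials exactly, so the planned data can separate switching from stopping. This also stands. What is missing is a written rule for reading the two results together.
- **The inflation is limited.** The closer the outcomes are to mirror images, the smaller it is. It nears 10% only when omissions separate them, and money then carries information of its own. This is correct and bounds the size of the problem without removing it: at no omission rate does the plan say what follows when the two results differ.

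Nor do the documents say that the team will present the two outcomes as separate confirmations. That is a risk left open, not a stated intention.

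**Conclusion.** The point holds in a limited form. Two correlated outcomes are named primary and each is tested at 0.05. Either can support a conclusion about cocaine, no rule links them, and the section 2 objective concerns cocaine only. The chance of a false zolmitriptan main effect on at least one is about 6-10% instead of 5%. That range rests on the last-completed-ratio reading and on assumed choice and omission rates. The documents give no such rates, so it is not an estimate for this trial.

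A reader might add up all the tests and blame the second outcome for the full-rule error of about 14-18%. The documents do not support that: about 10% arises on cocaine alone from accepting either a main effect or an interaction. That is a separate issue, and settling the primary outcome leaves it in place.

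The matter should be corrected before analysis. It does not threaten the design or the sample size.

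**What to change.** 1. In section 7 (Self-Administration Task and Data Analysis, Aim 1) and section 17, name cocaine break point as the single primary outcome, in line with section 2.
2. Name money break point as the key secondary outcome for Aim 1's reallocation hypothesis, tested at 0.05 only if the cocaine result is significant. Limit the inference about effects of cocaine to the cocaine outcome. This order restores 5% per effect. While the main-effect-or-interaction rule stays, the first step as a whole still runs at about 10%.
3. Conclude reallocation only if cocaine break point falls and money break point rises. The F tests are non-directional, so say that direction is read from the zolmitriptan dose means against placebo maintenance.
4. Define break point numerically, and report the number of omitted trials descriptively by zolmitriptan dose. Do not make an absence of increase in omissions a condition for reallocation: with 20 completers, a non-significant increase is not evidence of none.

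The cost is wording. No new data are needed, and power for the cocaine outcome is unchanged. The small downside is that a change seen only in money break point could not be called a primary result. Keeping both as primary at 0.025 each would also control the error, at the price in power shown in the working. Requiring both to succeed is another acceptable rule if the team prefers it.
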